5.2 Exclusion Criteria

Patients meeting any of the following exclusion criteria are not to be enrolled in the study.

1. Female patients who are lactating and breastfeeding or have a positive serum pregnancy test during the screening period.

2. Any serious medical or psychiatric illness that could, in the investigator's opinion, potentially interfere with the completion of treatment according to this protocol.
3. Treatment with any investigational products within 14 days before the first dose of study drug and systemic anticancer therapy within 28 days before the first dose of study drug
4. Untreated brain metastasis or history of leptomeningeal disease or spinal cord compression.
5. Tumors with involvement of the mediastinum.
6. Failure to recover from the reversible effects of prior anticancer therapies with the exception of alopecia, and after-effects associated with prior tyrosine kinase inhibitor therapy such as hair depigmentation, hypothyroidism, and/or splinter hemorrhage.
7. Systemic corticosteroid (inhalers are allowed) within 7 days before the first dose of study drug.
8. Manifestations of malabsorption due to prior GI surgery, GI disease, or for an unknown or other reason that may alter the absorption of MLN0128.
9. Diagnosis of diabetes mellitus; patients with a history of transient glucose intolerance due to corticosteroid administration may be enrolled if all other inclusion/exclusion criteria are met.
10. History of any of the following within 6 months before study entry:
 - Ischemic myocardial event, including angina requiring therapy and artery revascularization procedures
 - Ischemic cerebrovascular event, including transient ischemic attack and artery revascularization procedures
 - Requirement for inotropic support (excluding digoxin) or serious (uncontrolled) cardiac arrhythmia (including atrial flutter/fibrillation, ventricular fibrillation, or ventricular tachycardia)
 - Placement of a pacemaker for control of rhythm

- New York Heart Association Class III or IV heart failure
- Pulmonary embolism

11. Significant active cardiovascular or pulmonary disease at study entry, including:

- Uncontrolled high blood pressure (ie, systolic blood pressure > 180 mmHg, diastolic blood pressure > 95 mmHg)
- Resting pulse rate of < 50 beats per minute or > 100 beats per minute at screening or predose
- Pulmonary hypertension
- Uncontrolled asthma or O₂ saturation $< 90\%$ by arterial blood gas analysis or pulse oximetry on room air
- Significant valvular disease; severe regurgitation or stenosis by imaging independent of symptom control with medical intervention, or history of valve replacement
- Medically significant (symptomatic) bradycardia
- History of arrhythmia requiring an implantable cardiac defibrillator

12. Requirement for QT-prolonging drugs with a risk of causing torsades de pointes (TdP). Patients on a stable dose of drugs with a conditional or possible risk of QT prolongation may be considered.

13. Baseline prolongation of QTc (eg, repeated demonstration of QTcF > 430 ms for men and QTcF > 450 ms for women, or TdP); other abnormal ECG findings deemed clinically significant by the investigator or which would interfere with determination of the QT interval, such as bundle branch block, abnormal T waves or pathological U waves.

14. History of thoracic surgery, Brugada syndrome, history of congenital long QT syndrome (LQTS; or family history of LQTS), or major surgery within 14 days before the first dose of study drug

15. Clinically significant comorbidities such as uncontrolled pulmonary disease, active central nervous system disease, active infection, serious infection within 14 days before the first dose of study drug, or any other condition that could compromise study participation by the patient.
16. Patients requiring daily or chronic use of PPI and/or having taken a PPI within 7 days before receiving the first dose of study drug.

6. STUDY DRUG

6.1 Study Drug Administration

All protocol-specific criteria for administration of study drug must be met and documented prior to drug administration. Study drug will be administered only to eligible patients under the supervision of the investigator or identified sub-investigator(s).

MLN0128 is administered once weekly (QW) in continuous cycles of 28 days. MLN0128 will be supplied as capsules of 5 mg dose strength. All capsules will be swallowed whole. It is recommended that each dose of MLN0128 be given orally with 8 ounces (240 mL) of water.

Cycle 1, Day 1

During Holter ECG monitoring (Screening; Day -1 and Cycle 1, Day 1), patients will be given the option to report to the site fasted or after having a light morning meal, as long as the meal has been completed at least 2 hours before the scheduled baseline triplicate ECG on each day. If patients report to the site fasted, they should do so with adequate time (approximately 3 hours before the scheduled baseline triplicate ECG) to eat a light, standard breakfast provided by the site that will need to be completed at least 2 hours before the scheduled baseline triplicate ECG on each day. Patients will be instructed not to eat for the next 6 hours (ie, 2 hours before the 0-hour, predose time point and until completion of the collection of the 4-hour postdose PK/ECG assessments). A light, standard lunch will be provided at the same times on Screening; Day -1 and Cycle 1, Day 1.

On Cycle 1, Day 2 and Cycle 1, Day 3, patients may eat and drink up to approximately 2 hours before arriving at the study site for PK/ECG evaluations.

Patients will be required to swallow 8, 5mg capsules for a total dose of 40 mg MLN0128 on Cycle 1, Day 1. To mitigate nausea and vomiting known to occur at a 40 mg dose of MLN0128, patients will be administered an antiemetic agent (0.25 mg palonosetron), on

Cycle 1, Day 1, as an intravenous infusion over 30 seconds, at least 30 minutes before study drug administration.

Palonosetron is a commercially available drug; instructions are provided in the manufacturer's package insert.⁽¹²⁾

After Cycle 1, Day 3

After completing the required PK/ECG assessment period (Cycle 1, Day 3), patients may continue treatment with MLN0128 at the discretion of the investigator at a dose of MLN0128 30 mg QW. If patients experience severe emesis or mucositis preventing them from taking an MLN0128 dose, that dose will be skipped. If emesis occurs after study medication ingestion and whole capsule(s) are visible in the vomitus, replacement capsule(s) should be taken; otherwise the dose will not be re-administered, and patients should adhere to the dosing schedule and resume dosing at the next scheduled time with the prescribed dosage. Patients should record the time of the emesis in their dosing diary cards (see the Study Manual). Under no circumstance should a patient repeat a dose or double-up doses. Patients should be instructed to take their study medication at approximately the same time each week and not to take more than the prescribed dose at any time. Patients should swallow the study medication whole and not chew it, open it, or manipulate it in any way before swallowing. In the event, that, a patient fails to take the MLN0128 dose within the time frame specified (\pm 12 hours), that dose should be skipped. Patients should record any skipped doses in their dosing diary cards (see the Study Manual) and resume dosing at the next scheduled time with the prescribed dosage.

Starting at Cycle 1, Day 8, patients are advised to take their doses of study drug with a light meal.

6.2 Reference/Control Therapy

No reference or placebo treatment will be used in this study. All patients will receive treatment with MLN0128.

6.3 Definitions of Dose-Limiting Toxicity

Toxicity will be evaluated according to the NCI CTCAE, Version 4.03, effective 14 June 2010.⁽¹³⁾ These criteria are provided in the Study Manual. DLT will be defined as any of the following events that are considered by the investigator to be at least possibly related to therapy with MLN0128:

- Grade 3 or higher nonhematologic toxicity, despite adequate treatment, except for the following:
 - Grade 3 hyperglycemia lasting \leq 14 days (all patients should receive optimal antihyperglycemic treatment, including insulin).
 - Grade 3 rash lasting \leq 3 days (all patients should receive topical steroid treatment, oral antihistamines, and oral steroids, if necessary).
- Grade 4 neutropenia lasting $>$ 7 days in the absence of growth factor support.
- Grade 4 neutropenia of any duration accompanied by fever $\geq 38.5^{\circ}\text{C}$ and/or systemic infection.
- Any other \geq Grade 4 hematologic toxicity.
- Inability to administer at least 75% of planned doses of study drug within Cycle 1 due to treatment-related toxicity or delay in the initiation of the subsequent cycle of therapy by more than 14 days due to treatment-related toxicity (lack of adequate recovery of treatment-related hematological or nonhematological toxicities).
- Any clinically significant occurrence that the investigator and sponsor agree would place patients at an undue safety risk.

6.4 Dose-Modification Guidelines

MLN0128 is administered QW in continuous cycles of 28 days. Study drug should be administered continuously unless a \geq Grade 3 MLN0128-related event occurs.

For management of toxicity for individual patients, dose adjustments may include interruption of treatment with study drug and a dose reduction. If continued treatment with MLN0128 is thought to be beneficial by the investigator, and with the sponsor's approval, dose reductions should be based on the guidelines provided below and in [Table 6-1](#).

Patients whose dose is reduced will not be allowed to re-escalate.

Dosing should be interrupted for \geq Grade 3 MLN0128-related toxicities. If the event resolves to Grade 1 or baseline values within 14 days of interrupting treatment, depending on the severity of the toxicities, the patient may resume study drug as follows:

- Resume study treatment at 30 mg QW dose, or

MLN0128**Clinical Study Protocol C31002 Protocol Amendment 2**

- Resume study treatment at 20 mg QW (33% reduction)

If the toxicity recurs at the 20 mg QW dose, dosing should be interrupted. If the event resolves to Grade 1 or baseline values within 14 days of interrupting treatment, depending on the severity of the toxicity, the patient may resume study drug as follows:

- Resume study treatment at 20 mg QW, or
- Resume study treatment at 15 mg QW (25% dose reduction)

The sponsor's project clinician should be contacted before any dose modification of MLN0128 for any patient in the study.

Table 6-1 Dose Reduction Schedule for MLN0128

Dose Level	Percent Reduction	Dose
0	0%	30 mg QW
-1	33%	20 mg QW
-2	25%	15 mg QW

Abbreviation: QW = once weekly.

6.4.1 Criteria for Beginning or Delaying a Subsequent Treatment Cycle

MLN0128 is administered in continuous cycles; therefore, study drug should be administered continuously unless a \geq Grade 3 MLN0128-related event occurs. Patients who experience an AE meeting the definition for a DLT after Cycle 1, Day 3 should have their study drug treatment interrupted and reduced as outlined in Section 6.4.

6.4.2 Criteria for Dose Interruption During a Cycle

See Section 6.4 for dose modification guidelines.

6.4.3 Criteria for Dose Reduction

See Section 6.4 for dose modification guidelines.

6.4.4 Criteria for Discontinuation

Grade 4 nonhematologic toxicities will in general require that treatment with MLN0128 be permanently discontinued. If, in the opinion of the investigator and the project clinician, it is in the best interest of the patient to continue treatment with MLN0128, then the dose of

MLN0128**Clinical Study Protocol C31002 Protocol Amendment 2**

MLN0128 should be reduced by at least 1 dose level after recovery of the toxicity and/or intolerance to Grade 1 or to baseline values.

If dosing is delayed for > 14 consecutive days for MLN0128-related toxicities despite supportive treatment per standard clinical practice, or more than 2 dose reductions of MLN0128 are required for a patient, treatment should be stopped, the patient discontinued from the study, and the follow-up visit completed within 30 days of the last dose of MLN0128.

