6.8.2 Management of Hyperglycemia

In addition to obtaining fasting glucose levels at the clinic visits as outlined in the [Schedule of Events](#), all patients will be provided with a glucometer and trained to use it to monitor their daily predose FBG levels at home. Patients will be instructed to notify the study staff immediately of any abnormal readings (ie, ≥ 150 mg/dL) for further instructions on the management of their hyperglycemia. Hyperglycemia observed during home glucose monitoring should be confirmed in the clinic. Investigators will be responsible for reviewing the home glucose monitoring logs for hyperglycemia. If no irregularities in the FBG level are observed during a minimum of 6 consecutive months, then the frequency of in-home fasting glucose testing may be reduced to twice weekly if the investigator approves. Patients will continue to notify the investigator of FBG levels ≥ 150 mg/dL, and if blood glucose levels are not well controlled, or if they require either oral hypoglycemic agents or insulin to control blood glucose levels, then the frequency of in-home testing of FBG levels will be reinstated to daily. Guidelines for management of hyperglycemia are presented in [Table 6-3](#).

MLN0128
Clinical Study Protocol C31002 Protocol Amendment 2

Table 6-3 Management of Hyperglycemia

Grade	Description	Treatment	MLN0128 Dose Modification
1	FBG > ULN– 160 mg/dL	Continue close monitoring of blood glucose. Initiate oral hypoglycemic agent.	None
2	FBG > 160– 250 mg/dL	Initiate oral hypoglycemic agent and/or insulin if not well controlled on oral agent.	None
≥ 3	FBG > 250 mg/dL	Initiate oral hypoglycemic agent and/or insulin.	Hold drug until ≤ Grade 2. Resume MLN0128 based on timing of recovery: 
 • ≤ 1 week: resume at same dose and schedule • > 1 but ≤ 2 weeks: reduce by 20% • 2 weeks: stop MLN0128 and discontinue patient from the study

Prevention/Prophylaxis

- Follow fasting glucose levels during clinic visits.
- Monitor home glucometer test results.
- Check HbA1c levels every 3 months during therapy.
- Recommend lifestyle modifications, as appropriate (balanced diet, limited alcohol consumption, increased physical activity).
- Most episodes of Grade 1 and 2 hyperglycemia respond quickly to oral metformin. Early initiation of therapy is recommended to prevent higher grade hyperglycemia.

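### Table 6-3's ≥ 3 row lets a patient restart at full dose after Grade 4 hyperglycemia, which 6.4.4 does not allow; and the 20% cuts in Tables 6-3 to 6-6 cannot be made from whole 5 mg capsules

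*Protocol*

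**What the plan says.** **General rules (Protocol 6.4 to 6.4.4).** Section 6.4 holds dosing for drug-related toxicity of Grade 3 or higher and ties resumption to recovery: "If the event resolves to Grade 1 or baseline values within 14 days of interrupting treatment". After that it allows 30 mg or 20 mg weekly, then 20 mg or 15 mg on recurrence. It adds that "dose reductions should be based on the guidelines provided below" and in Table 6-1 (30, 20, 15 mg), with sponsor approval. Section 6.4.1 says that a DLT after Cycle 1, Day 3 leads to both interruption and reduction under 6.4. Section 6.4.4 is stricter for Grade 4: "Grade 4 nonhematologic toxicities will in general require that treatment with MLN0128 be permanently discontinued". If the investigator and project clinician prefer to continue, the dose of "MLN0128 should be reduced by at least 1 dose level after recovery of the toxicity and/or intolerance to Grade 1 or to baseline values". It also says that if "more than 2 dose reductions of MLN0128 are required for a patient, treatment should be stopped".

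**Event-specific tables (Protocol 6.8).** The top row of Table 6-3 is labelled ≥ 3 and covers any fasting glucose above 250 mg/dL. Its instruction is: "Hold drug until ≤ Grade 2. Resume MLN0128 based on timing of recovery". The first timing rule reads: "≤ 1 week: resume at same dose and schedule". Recovery in more than one and up to two weeks brings a 20% cut. Tables 6-2 and 6-6 also end in a ≥ 3 row. Tables 6-4 and 6-5 instead have a separate Grade 4 row that stops treatment. Twenty percent cuts appear in Tables 6-3, 6-4, 6-5 and 6-6.

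**The concern.** Two instructions apply to the same event and give different doses. After Grade 4 hyperglycemia, the table that a site would naturally open allows a full-dose restart while glucose is still Grade 2. Section 6.4.4 requires the drug to stop or, by exception, to restart lower and only after fuller recovery. Table 6-3 contains no pointer to 6.4.1 or 6.4.4, so the reader of the table is not warned.

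The 20% cuts raise a second, simpler problem. They name doses that cannot be dispensed and that lie outside the schedule in 6.4. Sites would have to round, and no rounding rule is given.

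At stake is the safety of patients who stay on weekly dosing after Cycle 1, Day 3. The primary QTc endpoint and the PK sampling are complete by then.

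**Working it through.** There is no statistical figure to reproduce. The check sets the rules side by side and does the dose arithmetic.

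**Inputs.** Dose levels 30, 20 and 15 mg weekly (Table 6-1). Four weekly doses per 28-day cycle (6.1). Capsules of 5 mg, swallowed whole (6.1). Hyperglycemia Grade 2 is > 160 to 250 mg/dL, and the ≥ 3 row is > 250 mg/dL (Table 6-3). Entry fasting glucose ≤ 120 mg/dL (5.1).

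**1. Grade 4 hyperglycemia that recovers to ≤ Grade 2 within a week.** Cycle totals are 4 × weekly dose.

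| Dose before event | Table 6-3 | 6.4.4 | Cycle total, Table 6-3 | Cycle total, 6.4.4 |
|---|---|---|---|---|
| 30 mg | 30 mg | 0, or at most 20 mg | 4 × 30 = 120 mg | 0 to 4 × 20 = 80 mg |
| 20 mg | 20 mg | 0, or at most 15 mg | 4 × 20 = 80 mg | 0 to 4 × 15 = 60 mg |
| 15 mg | 15 mg | 0 | 4 × 15 = 60 mg | 0 |

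The 15 mg line is zero because Table 6-1 has no lower level; for a patient already reduced twice, a third reduction also means stopping. The comparison covers events during weekly dosing. After the single 40 mg dose, continued dosing is capped at 30 mg, so a restart at 40 mg is already ruled out.

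**2. Does the qualifier in 6.4.4 reconcile the two?** The rule is stated as a general one, with an exception. The exception has two conditions: at least one dose level down, and recovery to Grade 1 or baseline. Table 6-3 meets neither.

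**3. Does another section settle it?** Section 6.3 makes related nonhematologic toxicity of Grade 3 or higher, despite adequate treatment, a DLT. For hyperglycemia it exempts only Grade 3 lasting up to 14 days. Section 6.4.1 then requires DLTs after Cycle 1, Day 3 to be interrupted and reduced. Grade 4 hyperglycemia that is a DLT is therefore directed to 6.4. If it falls outside the DLT definition because treatment was not yet adequate, 6.4.4 still covers it by grade. The direction exists, but only for a reader who starts from 6.4; Section 6.8.2 and Table 6-3 do not mention it.

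**4. Grade 3 hyperglycemia.** Section 6.4 itself allows resumption at 30 mg, so a same-dose restart at 30 mg is compatible with it. The only difference is the recovery grade. Table 6-3 permits dosing at > 160 to 250 mg/dL; 6.4 asks for Grade 1 or baseline, and baseline does not bridge the gap because entry requires ≤ 120 mg/dL.

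**5. Twenty percent cuts.**

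- 0.8 × 30 = 24 mg; 24 / 5 = 4.8 capsules. Nearest dose 25 mg, a cut of 5/30 = 16.7%.
- 0.8 × 20 = 16 mg; 16 / 5 = 3.2 capsules. Nearest dose 15 mg, a cut of 5/20 = 25%.
- 0.8 × 15 = 12 mg; 12 / 5 = 2.4 capsules. Nearest dose 10 mg, a cut of 5/15 = 33.3%.

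None is a whole number of capsules. The rounded doses of 25 mg and 10 mg are not Table 6-1 levels.

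**The case against.** The best defence is that the protocol already ranks its rules where it matters. Section 6.4.1 with 6.3 sends DLT-level hyperglycemia to 6.4, and 6.4.4 names Grade 4 nonhematologic toxicity expressly while Table 6-3 never does. That stands. A reader might infer that nothing in the protocol says which rule prevails; the documents do not support that for DLTs or for Grade 4 events. What remains is that the table contradicts those sections and does not point to them.

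A reader might also infer that resuming at ≤ Grade 2 is itself an error. The documents point the other way. Table 6-3 makes no dose change for Grade 2 hyperglycemia, and the text of 6.8.2 has it treated while MLN0128 continues. Table 6-6 makes no change for rash up to Grade 2. Section 6.4 holds dosing only from Grade 3. The two-week timetable in Table 6-3 also matches the 14-day exemption in 6.3. This is probably an intended exception that lacks a cross-reference.

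Third, there is oversight. Section 6.4 says that the sponsor's "project clinician should be contacted before any dose modification of MLN0128 for any patient in the study", and 6.4.4 involves the same clinician in any decision to continue after Grade 4. Since the hold sits in Table 6-3's dose-modification column, it would itself plausibly prompt that contact. An unreviewed full-dose restart is therefore unlikely. This lowers the risk but leaves the clinician with two conflicting texts.

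For the 20% cuts, 6.4 does supply deliverable levels. That shows which rule should win; it does not make the tables' instruction workable.

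**Conclusion.** The point holds in two parts. First, Table 6-3 contradicts 6.4.4, and 6.4.1 with 6.3, for Grade 4 hyperglycemia: 30 mg weekly against 0 or at most 20 mg, and correspondingly at the lower levels. Second, the 20% cuts in Tables 6-3 to 6-6 cannot be given as written and conflict with Table 6-1. The recovery grade in Tables 6-3 and 6-6 needs only a cross-reference.

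The conclusion rests on reading ≥ 3 with no glucose ceiling as including Grade 4. The protocol refers to CTCAE 4.03 for grading but does not reproduce it. For the same reason, whether the ≥ 3 rows for vomiting (Table 6-2) and rash (Table 6-6) have the same gap depends on whether CTCAE defines a Grade 4 for those events.

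The number of patients affected cannot be stated, because the documents give no event rates. It is likely small: Section 1.5 describes toxicities as mostly Grade 1 or 2, and 6.8.2 reports that hyperglycemia has not been dose-limiting since early treatment became standard. The QTc and PK results are not affected. This should be corrected as a safety instruction; it does not call the study's findings into question.

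**What to change.** 1. Split the ≥ 3 row of Table 6-3 into Grade 3 and Grade 4, with Grade 4 following 6.4.4. Tables 6-4 and 6-5 already have a Grade 4 row. Do the same in Tables 6-2 and 6-6 where CTCAE 4.03 defines a Grade 4.
2. Replace each 20% cut in Tables 6-3 to 6-6 with a reduction of one Table 6-1 dose level.
3. State in 6.4, and repeat in 6.8, that 6.4.1 and 6.4.4 govern DLTs and Grade 4 nonhematologic events, and that the event tables govern Grade 3 events that are not DLTs, including their ≤ Grade 2 recovery level. The sponsor should check the consequences for each table. For example, Grade 3 rash lasting more than 3 days is not exempt in 6.3, so where it is a DLT it would follow 6.4.

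The clinical content is for the sponsor to decide. The cost is amendment wording only, with no added procedures, visits or patients.

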6.5 Excluded Concomitant Medications and Procedures

The following medications and procedures are prohibited during the study:

- During the required PK/ECG assessment period (Cycle 1, Day 3), QT-prolonging drugs with a risk of causing TdP are prohibited. Patients on a stable dose of drugs with a conditional or possible risk of QT prolongation may be considered. (see Section 14.5).
- Radiation therapy for disease under study.
- Any investigational agent other than MLN0128 or mTOR inhibitors.
- Other anticancer therapies, including chemotherapy, immunotherapy, radioimmunotherapy, targeted agents, radiation, or surgery (patients can have palliative radiation or surgery during the study for pre-existing lesions).
- Systemic corticosteroids (either intravenous [IV] or oral steroids, excluding inhalers), unless necessary for treatment of an MLN0128-related AE (eg, rash).
- Anti-epileptic drugs for patients with a history of treated brain metastasis.
- Anti-emetic agents (eg, 5-HT3 receptor antagonists) associated with a risk for QT prolongation, including ondansetron and granisetron. After completing the required PK/ECG assessment period (Cycle 1, Day 3), treatment with granisetron is permitted according to standard of care.
- PPIs; examples of PPIs include: omeprazole, esomeprazole, lansoprazole, and pantoprazole.

- Strong cytochrome P450 (CYP) 1A2 inhibitors and CYP inducers should be administered with caution and at the discretion of the investigator. Refer to Section 14.4 for a list of these agents. Alternative treatments, if available, should be considered.

